9.2 Definition of the Days of Observation, Tests, and Sample Collection

The days of observation, tests, and sample collection will be defined as follows. [Table 9-1](#) shows the visit window of the assessment day.

9.2.1 Day of Informed Consent

The day when informed consent is obtained from the participant is defined as the day of informed consent.

9.2.2 Day of screening

The day of screening is defined as the day of first registration after completion of protocol-specified assessments. The day of informed consent may be the same day as the day of screening.

All observation/tests scheduled for the day of screening must be performed on the same day. The tuberculosis test may be performed after the day of screening; however, the test result should be reviewed before the day of study treatment initiation.

9.2.3 Day of Study Treatment Initiation

The day of study treatment initiation is defined as the day when the participant is enrolled after completion of protocol-specified assessments. All assessments scheduled for the day of study treatment initiation must be performed on the same day.

The day of study treatment initiation is Day 1, and the day before the day of study treatment initiation is Day -1.

9.2.4 Day of Assessment (Weeks 1, 2, 4, 8, 12, through 52)

Week 1 through Week 52 are days when participants visit the study site for protocol-specified observation/tests.

9.2.5 Day of Study Treatment

The day of study treatment is defined as the day when the IP is administered to the participant according to the schedule of [Table 9-1](#) after the protocol-specified assessments are implemented.

9.2.6 Day of Discontinuation

The day of discontinuation is defined as the day when the investigator or subinvestigator determines to withdraw the participant from the study.

9.2.7 Day of Discontinuation Visit

The day of visit for discontinuation is defined as the day when the protocol-specified observation/tests scheduled for discontinuation are performed for the participant who is determined to be withdrawn from the study after study treatment initiation and visit the study site for the procedure.

9.2.8 Day of Follow-up Visit

The day of follow-up visit is defined as the day when the protocol-specified observation/tests are performed for the participant who visits the study site 84 days (± 7 days) after the day of the last dose of study treatment.

9.3 Observation, Tests and Sample Collection

9.3.1 Participant Demographics

The investigator or subinvestigator will perform following assessments on the day of informed consent, the day of screening and the day of study treatment initiation.

- 1) Assessments on the day of informed consent
 - Primary disease (diagnosis)
 - Time of onset of primary disease
 - Classification of primary disease (diffuse cutaneous SSc [dcSSc] or limited cutaneous SSc [lcSSc])
 - Main therapy given for SSc in the past
 - Date of birth
 - Sex
 - Complication (any disease which is ongoing at the time of informed consent)
 - Race
 - Inclusion and exclusion criteria (see “4. Target Indication and Inclusion and Exclusion Criteria for Participants”)
- 2) Assessments on the day of screening
 - Inclusion and exclusion criteria (see “4. Target Indication and Inclusion and Exclusion Criteria for Participants”)
 - Height
- 3) Assessments on the day of study treatment initiation
 - Inclusion and exclusion criteria (see “4. Target Indication and Inclusion and Exclusion Criteria for Participants”)

9.3.2 Prior and Concomitant Medications and Therapies

9.3.2.1 Prior and concomitant medications

The investigator or subinvestigator will review the following medications for each participant:

- 1) Medications intended to treat SSc
 - Used from 28 days before the day of study treatment initiation to the physical examination at the follow-up visit
- 2) Medications intended to treat adverse events
 - a) Medications intended to treat adverse events of special interest defined in Section 11.6 :
 - Used from the day of study treatment initiation (after initiating study treatment) to the final outcome evaluation.
 - b) Medications intended to treat adverse events except for 1):
 - Used from the day of study treatment initiation (after initiating study treatment) to the physical examination at the follow-up visit.
- 3) All concomitant medications other than 1), and 2)
 - Used from the day of study treatment initiation (after initiating study treatment) to Week 52 or the day of discontinuation visit.

Information to be obtained	Presence or absence of concomitant medications, and the drug name, dosage, drug use classification, start and end dates of use, and indication for use of each concomitant medication
Notes	
The following information is not required to be collected:
 
 • Diagnostic agents, infusions, fluid replacement, nutritional agents, disinfectants, anesthetics for surgery, laxatives and suppository for barium examination (unless these drugs were used for treatment or are included in the prohibited concomitant medications) • Dosage of 3) • Among medications of 1), those newly used in participants who discontinued

	from the study on or after the physical examination at the discontinuation visit.
--	---

9.3.2.2 Prior and concomitant therapies

The investigator or subinvestigator will collect the data of the following therapies:

- 1) Therapies to treat SSc
 - Performed from 28 days before the day of study treatment initiation to the physical examination at the follow-up visit.
- 2) Concomitant therapies intended to treat adverse events
 - a) Concomitant therapies intended to treat adverse events of special interest defined in Section 11.6
 - Performed from the day of study treatment initiation (after initiating study treatment) to the final outcome evaluation.
 - b) Concomitant therapies intended to treat adverse events except for 1)
 - Performed from the day of study treatment initiation (after initiating study treatment) to the physical examination at the follow-up visit.
 - c) Prohibited concomitant therapies
 - Performed from the day of study treatment initiation (after initiating study treatment) to Week 52 or the day of discontinuation visit.

Information to be obtained	Presence or absence of therapy, and the name of therapy, site to which concomitant therapy is applied, start and end dates of application and purpose of use of concomitant therapy
Notes	Among therapies of 1), those newly performed to participants who discontinued from the study on or after the physical examination at the discontinuation visit are not required.

9.3.3 Body Weight

The investigator or subinvestigator will measure the body weight of participants at the following timepoints:

Data to be obtained	Body weight
Time points	Day of screening, Day of study treatment initiation, Week 4, 8, 12, 16, 20, 24, 28, 32, 36, 40, 44 and 48
Notes	
 • On the days of study treatment, measurement will be performed, and the results will be reviewed before administration of IP. • Participants weighing less than 30.0 kg on the day of study treatment are not allowed to receive study treatment.

9.3.4 Efficacy Evaluation

9.3.4.1 Evaluation of Skin Findings

The investigator or subinvestigator will perform the following assessments:

Assessment	mRSS
Time points	Day of screening, Day of study treatment initiation, Week 4, 12, 24, and 36, Week 52 or Day of discontinuation visit, Day of follow-up visit
Notes	
 • On the day of study treatment, assessment will be performed before the treatment. • mRSS assessment will be performed by a skilled physician experienced in scoring skin sclerosis. • In principle, the same investigator or subinvestigator will perform assessment throughout the study period for each participant in order to minimize inter-assessor variability.

9.3.4.2 Respiratory function test

Spirometry will be performed according to the separately specified procedure.

Assessment	
• Forced vital capacity (FVC) and %FVC• Diffusing capacity of lung for carbon monoxide (DLco) and % DLco• Total lung capacity (TLC) and forced expiratory volume in one second (FEV₁)
Time points	Day of screening, Week 12, and 24, Week 52 or Day of discontinuation visit
Notes	
• If the %FVC decreases by $\geq 15\%$ from baseline, %FVC will be measured again within 1 month to examine whether the %FVC decreases by $\geq 15\%$ from baseline or not.

9.3.4.3 Chest HRCT

HRCT will be performed according to the regulations or procedures or the test manual of the study site.

Time points	
• Day of screening, Week 24, Week 52 or Day of discontinuation visit
Notes	If having been performed within 1 month of the specified timepoint, it is not necessary to be performed at the specified timepoints, and the results within 1 month will be substituted.

9.3.4.4 Severity of pulmonary lesions

The investigator or subinvestigator will evaluate the severity of pulmonary lesions based on the results of respiratory function test and chest HRCT according to [10.1.4](#).

Time points	Day of screening, Week 24, Week 52 or Day of discontinuation visit
-------------	--

9.3.4.5 ACR-CRISS

The investigator or subinvestigator will assess whether the participant fall under the following criteria:

Evaluations	
• Onset of scleroderma renal crisis• Interstitial lung disease with a decline in %FVC $\geq 15\%$ (requiring reconfirmation within 1 month), and %FVC of 80% or less• Onset of left ventricular failure requiring treatment (defined as left ventricular ejection fraction $\leq 45\%$) *• Onset of pulmonary arterial hypertension requiring right heart catheterization * 
*Caused by SSc

Time points	Week 12 and 24, Week 52 or Day of discontinuation visit

9.3.4.6 The Number of Digital Ulcers

The investigator or subinvestigator will count the number of digital ulcers.

Time points	
• Day of screening, Day of study treatment initiation, Week 12, 24 and 36, Week 52 or Day of discontinuation visit
Notes	
• In principle, the same investigator or subinvestigator will perform assessment throughout the study period for each participant in order to minimize inter-assessor variability.

9.3.4.7 Patient-reported outcome

The participants will perform the following assessments:

Evaluations	HAQ-DI, FACIT-Fatigue and FSSG
Time points	Day of study treatment initiation, Week 12, 24, and 36, Week 52 or Day of discontinuation visit
Notes	
The participants will perform each assessment before receiving the examination and evaluation by the physician at the above visits.The investigator or subinvestigator must not attend the assessments by the participants.

9.3.4.8 Global improvement rating

9.3.4.8.1 Patient's Global Assessment (PtGA)

The participants will assess the overall condition of SSc using a visual analog scale (VAS).

Time points	Day of study treatment initiation, Week 12, 24, and 36, Week 52 or Day of discontinuation visit
Notes	
The participants will perform each assessment before receiving the examination and evaluation by the physician at the above visits.The investigator or subinvestigator must not attend the assessments by the participants.

9.3.4.8.2 Physician's Global Assessment (PGA)

The investigator or subinvestigator will assess the overall condition of SSc of each participant using a VAS.

Time points	Day of study treatment initiation, Week 12, 24, and 36, Week 52 or Day of discontinuation visit
Notes	
In principle, the same investigator or subinvestigator will perform assessment throughout the study period for each participant in order to minimize inter-assessor variability.

9.3.5 Safety Evaluation

9.3.5.1 Vital signs

The investigator or subinvestigator will perform the following measurements:

Measurements	Body temperature, pulse rate, and blood pressure (systolic/diastolic)
Time points	Day of screening, Day of study treatment initiation, Week 1, 4, 8, 12, 16, 20, 24, 28, 32, 36, 40, 44 and 48, Week 52 or Day of discontinuation visit, Day of follow-up visit
Notes	
On the day of study treatment, measurements will be performed, and the results will be reviewed before the treatment.The vital signs will be measured at rest in the sitting position.

9.3.5.2 ECG

The investigator or subinvestigator will perform the following measurements:

Measurements	PR interval, QRS interval, QT interval, heart rate and presence or absence of abnormalities
Time points	Day of screening, Week 24, Week 52 or Day of discontinuation visit

Notes	
 On the day of study treatment, measurements will be performed, and the results will be reviewed before the treatment. The same electrocardiograph will be used for each participant at each measurement whenever possible. ECG will be performed at rest in the supine position.
-------	--

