The investigator or subinvestigator will treat measurement results collected after the time of informed consent through the day of follow-up visit as AEs if the results meet any of the following criteria:

- i. Accompanied with clinical symptoms
- ii. Resulted in any change of study treatment (e.g., interruption or discontinuation of the IP).
- iii. Resulted in medical treatment (including change of concomitant medications/therapies).
- iv. Considered clinically significant by the investigator or subinvestigator.

d) Abnormal electrocardiograms

The investigator or subinvestigator will assess AEs based on the results collected after the time of informed consent through the day of follow-up visit

e) Echocardiography

Echocardiographic images will be assessed for cardiac morphology, cardiac motion and blood flow during cardiac contraction and relaxation, and other parameters. The investigator or subinvestigator will record the presence or absence of abnormalities in the source documents.

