17.3.3 Safety Analysis

The following variables will be summarized on the safety analysis set:

1) Adverse events

The following data will be collected and tabulated for AEs and separately for the treatment-related AEs.

- a) The number of participants included in the safety analysis set, and the number of participants with, and the number of occurrences of AEs, AEs by severity (mild, moderate, and severe), SAEs (total, fatal, and non-fatal), and AESIs will be calculated.
- b) The number of participants with AEs will be calculated by SOC and PT using MedDRA/J.
- c) For AESIs, the number of participants with AESIs, the number of participants with AESIs by PT will be calculated by the category.

2) Laboratory test values

- a) Laboratory test values throughout the treatment period

For the continuous variables, summary statistics will be calculated by laboratory parameter and time point. For the categorical variables, the number of participants will be calculated by category. The percentage of participants will be calculated using the number of observed participants at each time point.

- b) Changes in individual participants during the treatment period

A spaghetti plot will be created for each participant using individual test values by laboratory parameter of continuous variables.

3) Vital signs, physical findings, and other assessments related to safety

- a) Vital signs, electrocardiogram and echocardiography throughout the study period

For the continuous variables, summary statistics will be calculated by vital sign, electrocardiogram parameter, and echocardiography parameter. For the categorical variables, the number and percentage of participants will be calculated by category. The percentage of participants will be calculated using the number of observed participants at each time point.

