17.4 Determination of Sample Size

17.4.1 Target Sample Size

The target sample size for this study is 8 participants.

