17.4.2 Rationale for Sample Size

The number of participants required to determine the efficacy of this drug for SSc was set at 8. Since no statistical evaluation is planned, the number is not based on the level of significance and power.

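### The planned ECG summary names no heart-rate correction for QT, so QT change is confounded by heart-rate change; QTcF can be added from data already collected

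*Combined protocol and SAP*

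**What the plan says.** Section 9.3.5.2 (ECG) lists the measurements as "PR interval, QRS interval, QT interval, heart rate and presence or absence of abnormalities" and the time points as "Day of screening, Week 24, Week 52 or Day of discontinuation visit". On recording conditions it states that "ECG will be performed at rest in the supine position". It also asks for the same machine for a given participant where feasible, and for a pre-dose reading on dosing days.

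Section 17.3.3 3) (Safety Analysis) gives the analysis: "For the continuous variables, summary statistics will be calculated by vital sign, electrocardiogram parameter, and echocardiography parameter". That sentence names neither a derived QT variable nor a change from screening. Section 11.3 d) sets no numerical QT criterion for ECG adverse events: "The investigator or subinvestigator will assess AEs based on the results collected after the time of informed consent through the day of follow-up visit".

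The three protocol versions in the combined document read alike on these points. None mentions QTc, Fridericia or Bazett, and the visible abbreviation list has no QTc entry. The opening of Section 17 describes its content as the main plans and refers to a Statistical Analysis Plan for detail. The text supplied contains Section 17 but no standalone SAP.

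**The concern.** Measured QT depends on heart rate: it shortens when the heart speeds up and lengthens when it slows. Comparing uncorrected QT at Week 24 or Week 52 with screening therefore combines two things, a change in repolarisation and a change in resting rate. The summary can move when repolarisation has not changed, or stay flat when it has.

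Safety is a stated secondary objective and the ECG is a named safety assessment (Sections 2.2 and 11.1). Because Section 11.3 leaves ECG adverse events to investigator judgement, the summary in 17.3.3 3) is the only quantitative look at QT that the text plans. The individual plots in 17.3.3 2) b) cover laboratory values, not ECG. Both inputs to a correction are already recorded at every ECG, so the gap lies in the analysis, not in data collection.

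**Working it through.** **No plan figure to reproduce.** The documents give no QT value, and the sample size is not derived: "The target sample size for this study is 8 participants" and "Since no statistical evaluation is planned, the number is not based on the level of significance and power".

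**Inputs from the documents.** QT and heart rate are recorded at one screening ECG and at most two scheduled later ones, at rest and supine, and summarised by parameter.

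**Assumed inputs, not in the documents.** Corrected QT 380 to 420 ms; starting heart rate 60 to 80 bpm; a change of 5 or 10 bpm in either direction.

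**Method.** Hold corrected QT constant and calculate the QT that would be measured:

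- Fridericia: QT = QTc × (60/HR)^(1/3)
- Bazett, for comparison: QT = QTc × (60/HR)^(1/2)

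**Worked example.** QTc 400 ms, heart rate 70 to 80 bpm, Fridericia: 400 × (60/70)^(1/3) = 379.97 ms and 400 × (60/80)^(1/3) = 363.42 ms. QT falls by 16.5 ms with no repolarisation change. From 70 to 60 bpm it rises by 400 − 379.97 = 20.0 ms.

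**Range over the assumed inputs (absolute shift in QT).**

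| Heart-rate change | Fridericia, smallest | Fridericia, largest | Bazett range |
|---|---|---|---|
| 5 bpm | 6.9 ms (QTc 380, 80 to 85 bpm) | 12.4 ms (QTc 420, 60 to 55 bpm) | 9.8 to 18.7 ms |
| 10 bpm | 13.3 ms (QTc 380, 80 to 90 bpm) | 26.3 ms (QTc 420, 60 to 50 bpm) | 18.8 to 40.1 ms |

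**Masking.** Measured QT stays the same if heart rate rises to HR₀ × (new QTcF / old QTcF)³. From QTcF 400 ms at 70 bpm, a true 10 ms rise is hidden at 70 × (410/400)³ = 75.4 bpm, and a 20 ms rise at 70 × (420/400)³ = 81.0 bpm.

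**Effect on the group table.** The shifts above are for one participant. The mean of 8 moves by the full amount only if average heart rate moves by 5 or 10 bpm. If one participant of 8 changes by 10 bpm, the mean moves by 13.3/8 = 1.7 ms to 26.3/8 = 3.3 ms, although the minimum or maximum can move by the full shift.

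**The case against.** The strongest objection is that choosing a QT correction is ordinary SAP detail. Section 17 defers such detail, and Section 17.5 lets the analysis plan be settled at data review. This stands as a limit on the claim. A reader might infer that the sponsor will derive no corrected QT at all; the documents do not support that. They show only that none is named in the text supplied.

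A reader might also infer that the QT table could not be interpreted. That goes too far. Heart rate is an ECG parameter on the same list, so it is summarised too, and a reader can see whether the two moved together. Supine resting recordings limit rate variation, and abnormalities are recorded separately. Part of the point survives: separate summaries of QT and heart rate lose the pairing within each participant, so they do not yield corrected QT or its change. Supine rest also does not equalise heart rate across visits months apart.

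Materiality is low. With 8 participants, no control arm and at most two scheduled on-study ECGs, QTcF would still be an uncontrolled description and could not establish or exclude a drug effect. The adverse events of special interest in Section 11.2 include no QT or arrhythmia item. Nothing in the documents predicts a rise or fall in average heart rate, so the shifts above illustrate sensitivity and are not expected bias. All of this stands, and it sets the weight of the point.

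**Conclusion.** The point holds in a limited form. On the text supplied, QT is summarised as measured, with no rate correction named, so its change from screening is confounded by heart-rate change. Under the assumed values and Fridericia's formula, a 5 bpm change alone accounts for about 7 to 12 ms in a participant's QT and a 10 bpm change for about 13 to 26 ms. Those figures rest on assumed QTc and heart-rate ranges and would differ under another formula.

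This is a free improvement to a safety summary, not a defect in the trial. No data are lost, and the primary endpoint and sample size are unaffected. The conclusion would lapse if the separate SAP already names a correction.

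**What to change.** In Section 17.3.3 3), or in the SAP with a cross-reference, add: for each ECG, derive QTcF = QT / (60/heart rate)^(1/3) from that ECG's own QT and heart rate; summarise QTcF and its change from screening by time point, alongside uncorrected QT and heart rate. Uncorrected QT should stay in the table, since it is a protocol-listed measurement and shows what was observed.

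Name the formula before the data are reviewed. The Fridericia and Bazett columns above differ enough that choosing afterwards would leave room for selection. If the SAP already specifies a correction, a reference to it in 17.3.3 is enough.

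The cost is one derived variable and a few table rows. No new visit, measurement or participant burden is needed, and Section 17 fixes the analysis plan only before database lock.

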9.3.5.3 Echocardiography

Echocardiography will be performed according to the regulations, procedures, or the test manual of the study site.

Time points	Day of screening, Week 24, Week 52 or Day of discontinuation visit
Notes	
 On the day of study treatment, measurements will be performed, and the results will be reviewed before the treatment.

9.3.5.4 Photography

The investigator or subinvestigator will perform photography according to the separately specified procedure.

Sites to be Photographed	
 Anterior and dorsal views of the upper body (excluding the face) Skin appearance of adverse events
Time points	
 Day of study treatment initiation Duration of the following adverse events (at least once occurrence) after study treatment initiation and at the final outcome evaluation: 
 Atopic dermatitis Adverse events with skin symptoms accompanied by edematous erythema or scaling Any other adverse event for which the investigator or subinvestigator considers that photography is necessary.
Notes	
 1) and 2): 
 The photos will be retained by the study site and collected by the sponsor. When personal information can be identified from the photos, the photos must be collected with the personal information being masked. Photography will not be performed if refused by the participant.

